#### **8.7.4.2. Missing Severity**

If severity is missing for any AE, then its severity will be classified as missing in the summary tables.

#### **8.7.4.3. Missing Relationship**

If the assessment of relationship of the AE to study drug is missing for any AE, then it will be presented as missing in the listings and in the summary tables.

#### **8.7.5. Summaries of Adverse Event Incidence Rates for Serious Adverse Events (SAE), Adverse Event Dropouts, and Death**

During the treatment period, the number and percentage of subjects who experienced TESAEs (treatment emergent serious AEs) and separately TEAEs leading to withdrawal from the study will be presented by SOC and by PT within each SOC for each treatment. TESAEs and

separately TEAEs resulting in withdrawal from the study will be similarly presented by severity (mild, moderate, severe), by relationship to study drug (related would include definite, probable, and possible) and by outcome of events. Additionally, the number of TESAEs (as opposed to the number and percentage of subjects) and separately TEAEs leading to withdrawal will be presented.

Subgroup analyses for gender, race, and region are performed for AEs and SAEs leading to d/c. Analysis will be also done for subgroups of interest. Subgroups for age are defined based on the subject's age at Baseline. Details are provided in appendices.

In case that there are non-treatment emergent adverse events observed, the number and percentage of patients with all SAEs will be summarized by SOC and PT within each SOC. Additionally, the number of SAEs (as opposed to the number and percentage of subjects) will be presented.

A listing of all SAEs and discontinuations due to AEs will be included. Subject with deaths, SAEs, or subjects who withdraw due to AE will be listed separately and discussed with subject narratives.

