8.4. Withdrawal Criteria/Study Discontinuation

Patients may withdraw from the study at any time without stating a reason and without prejudice to further treatment. The Investigator may withdraw a patient from the study and discontinue study treatment and assessments at any time due to safety concerns or concerns about the patient's compliance with study requirements and procedures. Full skin examination will be performed at each visit. If SD-101 causes any significant rash that has not occurred previously in the patient, the Investigator should consider discontinuing the patient. In addition, if lesions appear to significantly worsen above the normal cycle seen in the patient, with use of SD-101, the Investigator should consider discontinuing the patient. If a patient discontinues treatment at any time after entering the study, the Investigator will make every effort to ensure the patient returns for all study visits.

Early discontinuation of any patient who has given informed consent/assent to participate will be recorded including the reason for discontinuation. The primary reason for a patient withdrawing prematurely will be selected from the following standard categories of early discontinuations.

1. Adverse Event (Adverse Reaction): Clinical events occurred or laboratory results are reported that in the medical judgment of the Investigator are grounds for discontinuation in the best interests of the patient.
2. Withdrawal of Consent: The patient desired to withdraw from further participation in the study. The patient is not obligated to provide any reason for withdrawal of consent, but where a reason is given this will be recorded on the eCRF.
3. Protocol Violation: The patient failed to adhere to the protocol requirements, at the Investigator's discretion.
4. Lost to Follow-Up: The patient stopped coming for visits and study personnel were unable to contact the patient.
5. Other: The patient was terminated for a reason other than those listed above, such as, termination of study by Sponsor or enrolled in the study by error when they did not meet inclusion/exclusion criteria.

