### **5.2. Changes from the Analyses Planned in the Statistical Analysis Plan**

The following changes were made to the analyses planned in the Version 6.0 of the SAP dated 12 May 2017:

- Wound age subgroup analysis is only conducted for  $\leq 30$  days and  $>30$  days subgroups.
- Subgroups of interest were defined post-database lock. These are;
  - Age of 2 years to  $<12$  years old
  - Wound age  $>30$  days
  - Total Body Wound Burden (TBWB)  $\geq 5\%$  at Baseline
  - Age of 2 years to  $<12$  years old plus TBWB  $\geq 5\%$  at Baseline
  - Age of 2 years to  $<12$  years old at Baseline plus RDEB.
- Subgroup analyses for gender, race, and region were not performed except for AEs and Serious Adverse Events (SAEs) leading to d/c (discontinuation).
- In general, subgroup analyses were performed only for the 6 "subgroups of interest" (ie, 2 to  $<12$  years, target wound age  $>30$  days, TBWB  $\geq 5\%$ , and the 2 combined groups as specified above with exception of demographics and some efficacy analyses. Details are provided in the appendices.
- Addition of time to event analysis truncated at Day 44.
- Addition of wound size reduction to efficacy analysis.
- Removal of some sensitivity analyses.
- Removal of subgroup analyses for itching and pain based on who was an evaluator.
- Addition of skin infection analysis.

The detailed list of tables and figures is provided in the appendices.

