### **8.7.3. Summaries of Adverse Event Incidence Rates for All Subjects**

The number and percentage of subjects who experienced TEAEs will be presented by system organ class (SOC) and by preferred term (PT) within SOC for each treatment group. TEAEs will be similarly presented by severity (mild, moderate, severe), by relationship to study drug (related would include definite, probable, and possible) and by outcome of events. Additionally, the number of TEAEs (as opposed to the number and percentage of subjects) will be presented by treatment group.

Analysis will also be done for subgroups of interest. Subgroups for age are defined based on the subject's age at Baseline. Details are provided in the appendices.

To count the number of subjects who experienced each TEAE, a subject experiencing the same TEAE multiple times will only be counted once for the corresponding PT. Similarly, if a subject experiences multiple TEAEs within the same SOC, the subject will be counted only once for that SOC. If a subject experiencing more than one TEAE within different severity or relationship categories within the same SOC/PT, only the worst case (worst severity and related TEAE) will be reported. TEAEs will be sorted alphabetically by SOC and within each SOC the PT will be presented by decreasing order of total frequency.

For TEAE summary by outcome, if a subject experienced more than one TEAE, the worst outcome will be counted under that subject. If a subject experienced more than one outcome within a SOC (or PT), the subject is only counted once under worst outcome in that SOC (or PT).

In addition, all adverse events will be provided by study site and by treatment group, in a listing, which will include the subject identifier, the PT, the reported term, the severity, the seriousness, the action taken, the outcome, the causality, the date onset, date of onset relative to the date of the first study drug administration, date of resolution, date of resolution related to the first study drug administration, and the TEAE duration (resolution date –onset date + 1). Separate listings will be provided for non-treatment emergent AEs, if any.

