Table 14.3.1.6.6.2	Number of Treatment-Emergent Adverse Events by EB Type, System Organ Class and Preferred Term (Safety Population)
Table 14.3.1.6.7.1	Incidence of Treatment-Emergent Adverse Events by Baseline BSAI of Total Body Wound Burden Group, System Organ Class and Preferred Term (Safety Population)
Table 14.3.1.6.7.2	Number of Treatment-Emergent Adverse Events by Baseline BSAI of Total Body Wound Burden Group, System Organ Class and Preferred Term (Safety Population)
Table 14.3.1.7.1	Incidence of Treatment-Emergent Adverse Events Leading to Discontinuation by System Organ Class and Preferred Term (Safety Population)
Table 14.3.1.7.2	Number of Treatment-Emergent Adverse Events Leading to Discontinuation by System Organ Class and Preferred Term (Safety Population)
Table 14.3.1.8.1	Incidence of Treatment-Emergent Serious Adverse Events Leading to Discontinuation by System Organ Class and Preferred Term (Safety Population)

Table Number	Table Title
Table 14.3.1.8.2	Number of Treatment-Emergent Serious Adverse Events Leading to Discontinuation by System Organ Class and Preferred Term (Safety Population)
Table 14.3.1.9.1	Incidence of Treatment-Emergent Adverse Events Leading to Discontinuation by Maximum Severity, System Organ Class and Preferred Term
Table 14.3.1.9.2	Incidence of Treatment-Emergent Serious Adverse Events Leading to Discontinuation by Maximum Severity, System Organ Class and Preferred Term (Safety Population)
Table 14.3.1.10.1	Incidence of Treatment-Emergent Adverse Events Leading to Discontinuation by Relationship to Study Drug, System Organ Class and Preferred Term (Safety Population)
Table 14.3.1.10.2	Incidence of Treatment-Emergent Serious Adverse Events Leading to Discontinuation by Relationship to Study Drug, System Organ Class and Preferred Term (Safety Population)
Table 14.3.1.11.1	Incidence of Treatment-Emergent Adverse Events Leading to Discontinuation by Outcome, System Organ Class and Preferred Term (Safety Population)
Table 14.3.1.11.2	Incidence of Treatment-Emergent Serious Adverse Events Leading to Discontinuation by Outcome, System Organ Class and Preferred Term (Safety Population)
Table 14.3.1.12.1.1	Incidence of Treatment-Emergent Adverse Events Leading to Discontinuation by Gender, System Organ Class and Preferred Term (Safety Population)
Table 14.3.1.12.1.2	Number of Treatment-Emergent Adverse Events Leading to Discontinuation by Gender, System Organ Class and Preferred Term (Safety Population)

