## 11.5 List of Listings

Listing Number	Listing Title
Listing 16.2.1	Patients Disposition (All Patients)
Listing 16.2.2	Protocol Deviations (ITT Population)
Listing 16.2.4.1	Demographics and Baseline Data (ITT Population)
Listing 16.2.4.2	Medical History (Safety Population)
Listing 16.2.6.1	Body Surface Area Index of Lesional Skin by Visit (ITT Population)
Listing 16.2.6.2	Body Surface Area Index of Total Body Wound Burden by Visit (ITT Population)
Listing 16.2.6.3	Itch Man Pruritus Assessment Tool (ITT Population)
Listing 16.2.6.4	FLACC Pain Scale (ITT Population)

Listing Number	Listing Title
Listing 16.2.6.5	Wong-Baker Faces Pain Scale (ITT Population)
Listing 16.2.7.1	Treatment-Emergent Adverse Events (Safety Population)
Listing 16.2.7.2	Non-Treatment Emergent Adverse Events (Safety Population)
Listing 16.2.7.3	All Serious Adverse Events (Safety Population)
Listing 16.2.7.4	All Treatment-Emergent Serious Adverse Events (Safety Population)
Listing 16.2.7.5	All Adverse Events Leading to Death (Safety Population)
Listing 16.2.7.6	All Adverse Events Leading to Discontinuation (Safety Population)
Listing 16.2.8	Pregnancy Test (All Female Patients of Childbearing Potential)
Listing 16.2.9	Vital Signs (Safety Population)
Listing 16.2.10	Target Wound Closure (ITT Population)
Listing 16.2.11	Prior and Concomitant Medications (Safety Population)
Ad-hoc Listing 16.2.12	Analysis Populations (ITT Population)
Ad-hoc Listing 16.2.13	Physical Examination (Safety Population)
Ad-hoc Listing 16.2.14	Exposure (Safety Population)
Ad-hoc Listing 16.2.15	Target Wound Characteristics Assessment (ITT Population)
Ad-hoc Listing 16.2.16	Target Wound Assessment of Scarring (ITT Population)

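### SAP 8.7.5 counts adverse events that lead to leaving the study, so an event that ends only the cream may reach no discontinuation table; the two outcomes need separate definitions and counts

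*SAP*

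**What the plan says.** SAP 8.7.5 gives the rule for these summaries: "separately TEAEs leading to withdrawal from the study will be presented by SOC and by PT within each SOC for each treatment". It names the study again as the thing left when it extends the summary to severity, relationship and outcome. Later in the same section the object disappears: "Subgroup analyses for gender, race, and region are performed for AEs and SAEs leading to d/c". SAP 5.2 spells out the abbreviation only as "leading to d/c (discontinuation"), again with no object.

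The outputs use the shorter term throughout. Table 14.3.1.7.1 in SAP 11.3 is titled "Incidence of Treatment-Emergent Adverse Events Leading to Discontinuation by System Organ Class and Preferred Term (Safety Population"), and the same phrase runs through to Table 14.3.1.12.7.4. Listing 16.2.7.6 in SAP 11.5 is "All Adverse Events Leading to Discontinuation (Safety Population"). Protocol 12.5 promises a summary of adverse events leading to withdrawal and does not say from what.

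Protocol 8.4 treats stopping treatment as something that need not end attendance: "If a patient discontinues treatment at any time after entering the study, the Investigator will make every effort to ensure the patient returns" for all visits. SAP 8.7.3 plans an adverse event listing whose columns include "the severity, the seriousness, the action taken, the outcome, the causality".

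**The concern.** In this trial, stopping the cream and leaving the study can be different events in the same patient, and the protocol asks sites to keep them apart. Someone who stops the cream for good because of an adverse event and attends through Visit 5 has done what Protocol 8.4 hopes for. On the literal wording of SAP 8.7.5 that patient has not withdrawn from the study, so the event is not counted. The more fully sites follow 8.4, the fewer events that ended treatment would be tabulated.

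Safety is part of the primary objective, and Protocol 11.2 names tolerability as a safety assessment. Adverse events that end use of a cream applied to the whole body bear directly on tolerability. A table that tracks loss to the study answers a different question.

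**Working it through.** The plan states no figure for this count, so there is none to reproduce. The check is a comparison of wording, followed by a scaling.

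**Step 1: follow one patient through the planned outputs.** Take a patient whose adverse event permanently ends the cream and who attends every remaining visit.

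- Text of SAP 8.7.5: not counted, because the patient did not leave the study.
- Disposition (SAP 8.1) and discontinuation summary (SAP 8.7.6): 8.1 takes the reason from the CRF termination page and 8.7.6 concerns leaving the study. Neither is planned to capture a stop of treatment alone.
- Treatment-emergent tables (SAP 8.7.3): the event is counted, by severity, relationship and outcome. No table in SAP 11.3 is organised by action taken.
- Adverse event listing (SAP 8.7.3): the event appears with its action taken.
- Exposure and compliance (SAP 8.7.1): fewer days of application show, but not the reason.
- Narratives (SAP 8.7.5): planned for deaths, serious events and withdrawals due to an adverse event, so a non-serious stop of treatment shares the same ambiguity.

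**Step 2: test the possible readings of the table titles.**

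- If the titles mean leaving the study, they agree with the 8.7.5 text, and this patient is in no discontinuation table.
- If the titles mean stopping the cream, this patient is counted, but the tables depart from the 8.7.5 text.
- If both mean stopping the cream, the patient is counted, and the 8.7.5 text says something it does not intend.

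Under every reading 8.7.5 is incomplete or wrong as written. Only under the first is the count lost.

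**Step 3: scale.** Inputs: 75 planned patients per arm (Protocol 12.1, SAP 4.4), assuming all are treated. Let *k* be the number in an arm who stop the cream for an adverse event but stay in the study. The documents give no value for *k*.

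- Change in that arm's incidence = *k*/75.
- *k* = 1: 1/75 = 1.3 percentage points.
- *k* = 5: 5/75 = 6.7 percentage points.
- Change in the difference between arms = (*k* in one arm − *k* in the other)/75. Equal *k* leaves the difference unchanged and lowers both rates. With 5 in one arm and 1 in the other, it is (5 − 1)/75 = 5.3 percentage points.

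The values 1 to 5 are assumptions to show the range, not estimates.

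**The case against.** A reader might infer that the SAP text and its table list hold two contradictory definitions and that the reported rates will be biased. The documents do not support either step.

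- The titles never say discontinuation of the cream. SAP 8.7.6 uses the word for leaving the study, and SAP 8.1 takes the reason for discontinuation from the termination page, so titles and text may well agree.
- The protocol's own vocabulary is loose. Section 8.4 couples withdrawal from the study with stopping treatment. Section 8.5, which is about withdrawals, also asks that patients return for all visits. Withdrawn and still attending can coexist there, and if sites completed the termination page whenever treatment stopped, the two counts could coincide.
- Protocol 13 lists intolerable adverse effects among the grounds for ending participation. Those terminations fall inside the 8.7.5 wording, so it would be wrong to say that the tables miss intolerance altogether.
- The events are not lost from the report, as step 1 shows.
- SAP 7.1 plans no formal inference on safety data.
- The CRF and its completion guide are not available, and either may settle the meaning.

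All of this stands as a limit on the point. It does not remove it. SAP 8.7.5 names the study twice as what is left, Protocol 8.4 foresees patients who stop treatment and stay, and no planned table is built on action taken. If text and titles agree in meaning the study, the gap runs through every discontinuation table.

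**Conclusion.** The point holds as an unclear safety count whose literal wording gives the less useful tolerability figure. An adverse event that permanently ends the cream but not participation is outside the 8.7.5 wording and, on that reading, in no discontinuation table. Each such patient is worth 1.3 percentage points in an arm of 75.

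This rests on the literal reading of 8.7.5 and on there being at least one such patient, which the documents neither show nor exclude. Understatement of the rate, or distortion between arms, is possible but not demonstrated; distortion needs unequal numbers of such patients in the two arms. Primary and secondary efficacy, alpha and power are unaffected. It is a cheap improvement.

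**What to change.** In SAP 8.7.5, define a treatment-emergent adverse event leading to discontinuation of study drug as one whose action-taken field records permanent discontinuation, whether or not the patient remains in the study. Use that definition for Tables 14.3.1.7 to 14.3.1.12 and Listing 16.2.7.6. Show treatment-emergent events leading to withdrawal from the study, taken from the termination page, as a separate count. Use the same two terms in SAP 5.2, 8.7.5 and the table and listing titles. Because the SAP amendment already carries changes made after database lock, date the clarification and mark it as such, so that the reading is not seen as chosen from the results.

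The cost is a short edit, retitled outputs and one derivation from a field already planned for the listing. It assumes that the field has a level for permanent discontinuation, which should be checked against the CRF. The discontinuation counts may become less favourable. The change concerns reporting only and alters no rule for stopping treatment.

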#### **8.7.6. Discontinuation from the Study**

Number of subjects who discontinued from the study and reasons for discontinuation will be summarized by treatment group.

#### **8.7.7. Clinical Laboratory Evaluations**

##### **8.7.7.1. Pregnancy Test**

Pregnancy test results will be listed for all female patients of child bearing potential only.

#### **8.7.8. Other Observations Related to Safety**

##### **8.7.8.1. Vital Signs**

Vital signs (weight, height/length, and temperature) conducted under the physical examination will be summarized using descriptive statistics for both actual results and change from Baseline for each treatment group. Vital Signs' assessments will also be presented in a listing. All vital signs will be presented using metric units.

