5. BACKGROUND INFORMATION

Epidermolysis Bullosa (EB) is a rare group of inherited disorders that typically manifest at birth as blistering and lesion formation on the skin and, in some cases, the epithelial lining of other organs, in response to little or no apparent trauma. In consequence, the skin is extremely fragile which can result in shearing of the skin, causing a high risk of infection. All forms of EB are both debilitating and life threatening. In some EB subtypes, high mortality occurs before the age of 1 (Junctional Herlitz), and others in adolescences to early adulthood, typically due to infection or failure to thrive. In addition, children surviving into their 20's and 30's are also at risk for development of a virulent form of squamous cell carcinoma, which is in many cases fatal.

There are no standard of care products available to treat the dermal manifestations of EB, and there is no approved drug for EB in either Europe or the United States. There have been numerous studies published on potential treatments for skin manifestations associated with EB, including vitamin E therapy, systemic phenytoin, topical nonsteroidal agents, cyproheptadine, tetracycline, and dapsone. No controlled studies showed clinical benefit of any therapy. Newer exploratory treatments including skin grafts, bioengineered skin products, and gene therapy have been unsuccessful to date.

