8.2. Inclusion Criteria

Patients must meet all of the following inclusion criteria to be eligible for enrollment into the study.

1. Informed Consent form signed by the patient or patient's legal representative; also, if the patient is under the age of 18 but capable of providing assent, signed assent from the patient.
2. Patient (or caretaker) must be willing to comply with all protocol requirements.
3. Diagnosis of Simplex, Recessive Dystrophic, or Junctional non-Herlitz EB.
4. Patient must have 1 target wound (size 10 to 50 cm²).
5. Patients 1 month and older.
6. Target wound must be present for 21 days or more.

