12.5. Statistical Methods for Safety Parameters

Adverse events will be coded using MedDRA. The number of events, incidence, and percentage of treatment-emergent AEs (TEAE) will be calculated overall, by system

organ class (SOC), and by preferred term. Treatment-emergent AEs will be further summarized by severity and relationship to investigational product. Adverse events related to investigational product, AEs leading to withdrawal, SAEs, and deaths will be summarized.

Baseline and Month 3 physical examination results, together with changes during the study period, will be described using summary statistics.

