#### **6.4.3. Vital Signs**

Vital signs (temperature, height/length, and weight) are a part of the physical examination, which will be performed at the Screening visit and Month 3/ Final visit. All vital signs will be reported in metric units.

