### **7. STATISTICAL METHODS**

#### **7.1. General Methodology**

For statistical analysis purposes, Baseline is defined as the last measurement prior to the first application of the study drug.

In general, no formal inferential analyses are planned for the Baseline and safety data, and only descriptive statistics will be provided.

For the descriptive statistics, the categorical variables will be summarized by frequency and percentage for each response category (number of patients, %) and the continuous variables will be summarized using means, medians, minimum, maximum, and standard deviations.

Data will be summarized by treatment groups, and overall (where appropriate).

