### **8.2. Demographic and Other Baseline Characteristics**

Descriptive summaries of demographic and Baseline characteristics will be presented for the ITT and SAF populations. If the ITT and the SAF populations are identical, then the summaries will be based on ITT population only.

Continuous variables such as patient age, weight, height/length, body mass index (BMI), body surface area (BSA) calculated by Mosseler formula, body surface area index BSAI (for lesion and wound burden), age of target wound, target wound size, and temperature will be summarized as described previously.

Categorical variables such as patient gender, race, and age (0 to 27 days, 28 days to < 2 years, 2 years to < 12 years, 12 years to < 18 years, ≥ 18 years), age of target wound (≤ Median, > Median; and 0 ≤ 30 days, 31 ≤ 60 days, 61 ≤ 90 days, > 90 days), will be summarized using number of observations and percentages for each category.

Demographics is also presented for subgroups of interest.

Medical history, including disease history and EB type, will be summarized and listed.

Age will be defined as follows:

- If age was collected instead of the birth date then, the collected value will be used,
- If the birth date was collected, then

Age = (date of informed consent date - date of birth + 1) / 365.25 and truncated to completed years.

Weight will be displayed in kg, height/length will be displayed in centimeters (cm), and temperature will be displayed in degrees Celsius (°C).

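### Weight and height/length are summarised as raw change pooled from infants to adults, so the vital-signs table cannot show children who grow less than expected

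*SAP*

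**What the plan says.** Protocol 8.2 admits "Patients 1 month and older" and sets no upper age limit. Weight, height/length and temperature belong to the physical examination, "which will be performed at the Screening visit and Month 3/ Final visit" (SAP 6.4.3). There are therefore two measurements per patient, about 90 days apart.

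The analysis is in SAP 8.7.8.1: these measurements "will be summarized using descriptive statistics for both actual results and change from Baseline for each treatment group", with a listing as well. SAP 7.1 fixes the statistics: "continuous variables will be summarized using means, medians, minimum, maximum, and standard deviations". Protocol 12.5 is no more specific: "Baseline and Month 3 physical examination results, together with changes during the study period, will be described using summary statistics". The table list in SAP 11.3 has one vital-signs table, 14.3.3.1, in the Safety population, with no version by age group or subgroup.

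SAP 8.2 defines five age bands: 0 to 27 days, 28 days to under 2 years, 2 to under 12 years, 12 to under 18 years, and 18 years and over. Baseline characteristics are tabulated by age group (Ad-hoc Table 14.1.2.2), and so are treatment-emergent adverse events (Tables 14.3.1.6.2.1 and 14.3.1.6.2.2). Neither document plans a z-score, percentile or growth velocity. BMI appears only as a baseline characteristic.

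**The concern.** Over 90 days an infant is expected to gain weight and length, and an adult is not. One mean of raw change over both mixes expected growth with departures from it. A child who gains less than expected contributes a positive number, and a child who gains nothing contributes the same number as a stable adult.

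Growth matters in this disease. Protocol section 5 describes deaths in EB as "typically due to infection or failure to thrive", and Appendix 1 lists malnutrition as a complication of both recessive dystrophic and non-Herlitz junctional EB, which are enrolled types. The safety assessments are tolerability, adverse events and physical examination, and the only laboratory evaluation in the SAP is a pregnancy test. Weight and height/length are therefore among the few numerical safety measurements. What is at stake is whether the planned summary could show a difference between arms in children's growth if one existed.

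**Working it through.** The plan states no growth figure, so there is nothing of its own to reproduce. The check has three parts.

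**1. What the table can contain.** Inputs: one table, by arm, all ages, raw value and raw change (SAP 8.7.8.1, SAP 11.3); mean, median, minimum, maximum and SD (SAP 7.1). If a child's expected gain is g > 0 and the child achieves a fraction f of it, with 0 < f < 1, the recorded change is f × g, which is positive. The shortfall is g × (1 − f). It is not recorded anywhere in the table, because g does not enter the analysis.

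**2. How far a shortfall would move the all-ages comparison.** This illustration is for weight only. Every input except the 75 per arm is an assumption:

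- share of infants s = 5%, 10% or 20% in each arm
- expected infant gain over 90 days g = 1.0 or 2.0 kg
- infants in one arm achieve f = 25%, 50% or 75% of g; infants in the other arm achieve all of it
- SD of change 0.3 kg in infants and 1.5 kg at other ages; mean change at other ages 0.5 kg in both arms

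Formulas:

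- All-ages arm difference = s × g × (1 − f)
- Variance of change = s × 0.3² + (1 − s) × 1.5² + s(1 − s)(g − 0.5)²
- All-ages standard error = √(2 × variance / 75)
- Within infants: difference = g × (1 − f), standard error = √(2 × 0.3² / (75 × s))

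Selected results:

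| s | g (kg) | f | Infant change shown (kg) | All-ages difference / SE (kg) | Ratio | Within-infant difference / SE (kg) | Ratio |
|---|---|---|---|---|---|---|---|
| 5% | 1.0 | 75% | +0.75 | 0.013 / 0.240 | 0.05 | 0.25 / 0.22 | 1.1 |
| 10% | 1.0 | 50% | +0.50 | 0.050 / 0.234 | 0.21 | 0.50 / 0.15 | 3.2 |
| 10% | 2.0 | 50% | +1.00 | 0.100 / 0.244 | 0.41 | 1.00 / 0.15 | 6.5 |
| 20% | 2.0 | 25% | +0.50 | 0.300 / 0.241 | 1.24 | 1.50 / 0.11 | 13.7 |

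Over all 18 combinations the under-growing infants show a mean change of +0.25 to +1.50 kg. The all-ages ratio runs from 0.05 to 1.24, and the within-infant ratio from 1.1 to 13.7.

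Two cautions apply. The assumed 1.5 kg SD supplies most of the all-ages variance: in the first row 0.95 × 2.25 = 2.138 of 2.154, in the last 0.80 × 2.25 = 1.80 of 2.178. The ratios therefore rise if that SD is smaller. The variance formula also uses the full gain g in both arms. In the last row, using the reduced gain in the affected arm gives a variance of 0.018 + 1.80 + 0 = 1.818 there, an SE of √((2.178 + 1.818)/75) = 0.231 kg and a ratio of 1.30 in place of 1.24.

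**3. Whether age bands alone suffice.** Given the entry criterion, the 0 to 27 day band should be empty. The next band runs from 28 days to under 2 years and still combines very different expected growth. Bands remove the mixing of children with adults. Only a comparison with expected growth for age and sex removes it within a band.

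**The case against.** Growth is not an objective or endpoint, and no passage links the cream to it; Protocol 5.2 reports no systemic effects in topical toxicology studies. The background sentence on failure to thrive describes the disease, and its context includes Junctional Herlitz EB, which is not enrolled. Safety analysis is declared descriptive, and other routes exist: Listing 16.2.9 gives every value, the minimum can reveal a loss, physical examination has normal/abnormal shift tables, and clinically relevant worsening that meets the adverse event definition must be reported. All of this stands. It limits the size of the point but does not remove it, because none of these routes compares growth with what is expected, and the minimum may belong to an adult.

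A reader might infer more than the documents support:

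- **That poor growth is reported as normal, or that the data are lost.** Raw change is reported as raw change, nothing labels it normal, and the individual values are kept.
- **That every infant is analysed with age 0.** SAP 8.2 has age "truncated to completed years" only where it is derived from a birth date; a collected age is used as recorded. Age does not enter SAP 8.7.8.1 at all, so truncation does not cause the gap. It matters only for how a fix is programmed.
- **That raw change reflects age mix more than health, so chance age imbalance distorts the arm comparison.** Assume age shares of 10/50/15/25% (under 1, 1-11, 12-17, adult) and gains of 1.2/0.6/1.1/0 kg. The mean is 0.585 kg and the between-age SD is √(0.5055 − 0.585²) = 0.404 kg. With 75 per arm, chance imbalance then has a standard error of 0.404 × √(2/75) = 0.066 kg, which is small. With no within-age SD in the documents, the comparison with health cannot be made.

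**Conclusion.** The point holds as a gap in the planned summaries. The by-arm table of raw values and raw change, pooled from 1 month of age to adulthood, cannot distinguish expected growth from growth below expectation.

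That conclusion follows from the structure of the table and needs no assumed figure. The size does rest on assumptions: the age mix, expected gains and SDs in the illustration are not in the documents. Under them, a shortfall of 25-75% in one arm's infants would usually be well under one standard error in the all-ages table. At the low end (5% infants, about 4 per arm) it could be as little as 1.1 standard errors even within infants, so the gain from a fix is uncertain if few infants were enrolled.

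The point is minor. It touches no primary or key secondary endpoint, alpha or power, and it is not evidence that the treatment affects growth.

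**What to change.** In SAP 8.7.8.1, present Table 14.3.3.1 by the SAP 8.2 age bands, with adults separate. For patients under 18, add age- and sex-standardised z-scores for weight and height/length at Baseline, at Month 3 and as change, by arm. Name the growth reference in the SAP, and compute exact age at each visit from date of birth where available, not from age in completed years. No fixed z-score cut-off is proposed, since the documents give no basis for one.

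The cost is one derivation and a few table pages. Sex, weight and height/length are already collected, and Protocol 15.5 requires date of birth in the patient file. The drawbacks are small numbers in the youngest bands and no z-score where the birth date cannot be obtained. Because the current SAP amendment already follows database lock, an addition now should be labelled as post-lock and descriptive. If only one step is taken, splitting the existing table by age band is the cheaper one.
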